**Global health status:**

- Global health status/QOL:  $((Q29+Q30)/2-1)/6 * 100$

**Symptom scales/Items:**

- Fatigue:  $((Q10+Q12+Q18)/3-1)/3 * 100$
- Nausea and vomiting:  $((Q14+Q15)/2-1)/3 * 100$
- Pain:  $((Q9+Q19)/2-1)/3 * 100$
- Dyspnoea:  $((Q8-1)/3 * 100$
- Insomnia:  $(Q11-1)/3 * 100$
- Appetite loss:  $(Q13-1)/3 * 100$
- Constipation:  $(Q16-1)/3 * 100$
- Diarrhoea:  $(Q17-1)/3 * 100$
- Financial difficulties:  $(Q28-1)/3 * 100$

The QLQ-H&N 35 EORTC module will also be used to assess health-related quality of life. Eighteen scales are derived from the 35 questions of the QLQ-H&N 35 EORTC module :

- Seven multi-item scales that assessed Pain, Swallowing, Senses, Speech, Social eating, Social contact and Sexuality.
- Eleven single item : Teeth, Opening mouth, Dry mouth, Sticky saliva, Coughing, Feeling ill, Use of pain killers, Use of nutritional supplement, Use of feeding tube, Lost of weight and Gain of weight.

Each scale in the QLQ-H&N 35 EORTC questionnaire will be scored (0 to 100).The scoring approach for the QLQ-H&N35 is identical in principle to that for the symptom scales /single items of the QLQ-C30 and is summarized below. In this summary Qi refers to the  $i^{\text{th}}$  question on the QLQ-H&N 35 EORTC.

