11.5. CLINICAL STATISTICAL METHODS

11.5.1. Statistical methodology

The statistical analysis will be performed by Institut de Recherche Pierre Fabre. Data will be analysed using the SAS[®] system software version 8.2 (or later if available) for Windows[®]. All statistical tests will be two-sided at a 5% level of significance unless otherwise specified.

Summary tables will be provided according to the standard format of Institut de Recherche Pierre Fabre developed for the vinflunine chemotherapy.

Continuous data will be summarized with the following items: frequency, median, (if $n \geq 3$), range and mean and standard error if relevant.

Categorical data will be presented in contingency tables with frequencies and percentages of each modality (including missing data modality).

Whatever the number of events at the end of study, the final analysis of OS (primary analysis) will be performed on ITT population.

Only descriptive analyses will be performed on all secondary efficacy analyses for ITT population (secondary analyses on primary and secondary parameters, subgroup analyses, QoL).

Safety analyses will be performed as planned.

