11.5.5.2. Health-related quality of life analyses

The analysis of health-related quality of life will be done on the evaluable population for quality of life. Compliance with the questionnaires will be displayed per evaluation. Compliance is defined as the number of forms actually received as a proportion of those expected. The number of QoL questionnaires completed and evaluable per evaluation will also be given. The number of patients non evaluable for health-related quality of life analysis and reasons for non-evaluability will be tabulated.

Each parameter will be described at baseline. Changes of the scores from baseline of the parameters (15 for QLQ-C30 and 13 for QLQ-H&N 35) will be provided. Figures will be displayed in order to show the evolution of each scale.

A repeated measure analysis will be performed for all scales and single items with change from baseline as the response.

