29. How would you rate your overall health during the past week?

1 2 3 4 5 6 7

Very poor

Excellent

30. How would you rate your overall quality of life during the past week?

1 2 3 4 5 6 7

Very poor

Excellent

EORTC QLQ - H&N35

Patients sometimes report that they have the following symptoms or problems. Please indicate the extent to which you have experienced these symptoms or problems during the past week. Please answer by circling the number that best applies to you.

During the past week:

	Not at all	A little	Quite a bit	Very much
31. Have you had pain in your mouth?	1	2	3	4
32. Have you had pain in your jaw?	1	2	3	4
33. Have you had soreness in your mouth?	1	2	3	4
34. Have you had a painful throat?	1	2	3	4
35. Have you had problems swallowing liquids?	1	2	3	4
36. Have you had problems swallowing pureed food?	1	2	3	4
37. Have you had problems swallowing solid food?	1	2	3	4
38. Have you choked when swallowing?	1	2	3	4
39. Have you had problems with your teeth?	1	2	3	4
40. Have you had problems opening your mouth wide?	1	2	3	4
41. Have you had a dry mouth?	1	2	3	4
42. Have you had sticky saliva?	1	2	3	4
43. Have you had problems with your sense of smell?	1	2	3	4
44. Have you had problems with your sense of taste?	1	2	3	4
45. Have you coughed?	1	2	3	4
46. Have you been hoarse?	1	2	3	4
47. Have you felt ill?	1	2	3	4
48. Has your appearance bothered you?	1	2	3	4

During the past week:

	Not at all	A little	Quite a bit	Very much
49. Have you had trouble eating?	1	2	3	4
50. Have you had trouble eating in front of your family?	1	2	3	4
51. Have you had trouble eating in front of other people?	1	2	3	4
52. Have you had trouble enjoying your meals?	1	2	3	4
53. Have you had trouble talking to other people?	1	2	3	4
54. Have you had trouble talking on the telephone?	1	2	3	4
55. Have you had trouble having social contact with your family?	1	2	3	4
56. Have you had trouble having social contact with friends?	1	2	3	4
57. Have you had trouble going out in public?	1	2	3	4
58. Have you had trouble having physical contact with family or friends?	1	2	3	4
59. Have you felt less interest in sex?	1	2	3	4
60. Have you felt less sexual enjoyment?	1	2	3	4

During the past week:

	No	Yes
61. Have you used pain-killers?	1	2
62. Have you taken any nutritional supplements (excluding vitamins)?	1	2
63. Have you used a feeding tube?	1	2
64. Have you lost weight?	1	2
65. Have you gained weight?	1	2

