### **Single items:**

Teeth:	$(Q9-1)/3 * 100$
Opening mouth:	$(Q10-1)/3 * 100$
Dry mouth:	$(Q11-1)/3 * 100$
Sticky saliva:	$(Q12-1)/3 * 100$
Coughing:	$(Q15-1)/3 * 100$
Felt ill:	$(Q17-1)/3 * 100$
Pain killers :	$(Q31-1)/3 * 100$
Nutritional supplements:	$(Q32-1)/3 * 100$
Feeding tube:	$(Q33-1)/3 * 100$
Weight loss:	$(Q34-1)/3 * 100$
Weight gain:	$(Q35-1)/3 * 100$

If a question was filled in by circling more than one answer, the internal convention at Pierre Fabre is to consider the answer as missing.

A questionnaire is considered to be completed if more than two thirds of the questions are answered. Otherwise the questionnaire is ignored for the analysis.

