#### **6.2.2. Secondary parameter**

The secondary quality of life parameters will be the fourteen other scales of QLQ-C30 questionnaire and the eighteen scales of the QLQ-H&N 35 EORTC. Each analysis will be presented by functional and/or "symptoms" scales for QLQ-C30 questionnaire and by multi-items scales and/or single items for the QLQ-H&N 35 EORTC.

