### 12.1.2. Descriptive analyses

The number of QoL questionnaires completed and evaluable per evaluation will also be given.

The quality of life will be assessed (using the EORTC questionnaires, without any medical staff influence) at baseline before randomisation, every 6 weeks during the study and at the end of treatment evaluation (within 30 days of the last dose administration).

Missing data is a typical problem of QoL analysis. There are two levels of missing data :

- Missing item(s) in a questionnaire filled in by the patient,
- Completely missing questionnaire at a given evaluation.

For the first level, if more than one third of the items is missing then the questionnaire is non-evaluable.

Each parameter will be described at baseline. Changes of the scores from baseline of the parameters (15 for QLQ-C30 and 13 for QLQ-H&N 35) will be provided for each (mean, standard deviation, median, Q1, Q3, minimum and maximum).

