14.4.1b	Concomitant medications whatever the indication per cycle [ITT]	14_4_1b.RTF
14.4.2a	Concomitant medications with a tumour related indication per patient [ITT]	14_4_2a.RTF
14.4.2b	Concomitant medications with a tumour related indication per cycle [ITT]	14_4_2b.RTF
14.4.3a	Concomitant medications with a prophylactic indication per patient [ITT]	14_4_3a.RTF
14.4.3b	Concomitant medications with a prophylactic indication per cycle [ITT]	14_4_3b.RTF
14.4.4a	Concomitant medications with pre-treatment event indication per patient [ITT]	14_4_4a.RTF
14.4.4b	Concomitant medications with pre-treatment event indication per cycle [ITT]	14_4_4b.RTF
14.4.5a	Concomitant medications with medical history indication per patient [ITT]	14_4_5a.RTF
14.4.5b	Concomitant medications with medical history indication per cycle [ITT]	14_4_5b.RTF
14.5	EORTC QLQ-C30 (Global Health Status) : Values and changes from baseline Over Time and at last cycle [Evaluable Pop for QLQ-C30]	14_5_1a.RTF
14.5	EORTC QLQ-C30 (Functional scales): Values and changes from baseline Over Time and at last cycle [Evaluable Pop for QLQ-C30]	14_5_1b.RTF
14.5	EORTC QLQ-C30 (Symptom Scales/Items) : Values and changes from baseline Over Time and at last cycle [Evaluable Pop for QLQ-C30]	14_5_1c.RTF
14.5	QLQ-Head and Neck EORTC 35 Module (Multi-item scales) : Values and changes from baseline Over Time and at last cycle [Evaluable Pop for QLQ-H&N 35]	14_5_2a.RTF
14.5	QLQ-Head and Neck EORTC 35 Module (Single items) : Values and changes from baseline Over Time and at last cycle [Evaluable Pop for QLQ-H&N 35]	14_5_2b.RTF
16.2.1	Discontinued patients	16_2_1_1.RTF
16.2.1	Follow-Up data	16_2_1_2.RTF
16.2.2	Protocol Deviations at study entry	16_2_2_1.RTF
16.2.2	Protocol Deviations on treatment	16_2_2_2.RTF
16.2.3	Analysis sets	16_2_3_1.RTF
16.2.3	Eligibility criteria	16_2_3_2.RTF
16.2.3	Randomization criteria	16_2_3_3.RTF
16.2.4	Patients' characteristics	16_2_4_1.RTF
16.2.4	Disease characteristics	16_2_4_2.RTF
16.2.4	Prior surgery for SCCHN	16_2_4_3a.RTF
16.2.4	Prior radiotherapy for SCCHN	16_2_4_3b.RTF
16.2.4	Prior chemotherapy for SCCHN	16_2_4_3c.RTF
16.2.4	Prior treatment for SCCHN	16_2_4_3d.RTF
16.2.4	Medical and Surgical History, Concomitant disease	16_2_4_4.RTF
16.2.4	Pre-treatment events	16_2_4_5.RTF
16.2.4	Blood and Platelet transfusion	16_2_4_6.RTF
16.2.5	Treatment administration of Vinflunine	16_2_5_1.RTF

SECTION	Title	RTF reference
16.2.5	Treatment administration of Methotrexate	16_2_5_2.RTF

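### Five yes/no items of the QLQ-H&N35 (Q31 to Q35) are scored with the four-point divisor, so a Yes scores 33.3 and the stated 0 to 100 range cannot be reached

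*SAP*

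**What the plan says.** SAP 6.2 lists eighteen scales for the head and neck module, seven multi-item and eleven single-item, and states that each scale in the QLQ-H&N "35 EORTC questionnaire will be scored (0 to 100"). It defines Qi as the i-th question of the module. Under the heading Single items, all eleven get the same formula, (Q − 1)/3 × 100. These include Q31 (pain killers), Q32 (listed as "Nutritional supplements"), Q33 (feeding tube), Q34 (weight loss) and Q35 (weight gain).

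Protocol Appendix 7 prints the module as items 31 to 65, so module question i is printed as item i + 30. Items 61 to 65, for example "Have you taken any nutritional supplements (excluding vitamins"), stand under the column heads No and Yes with codes 1 and 2. The other module items are coded 1 to 4.

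On reporting, SAP 6.2.2 says: "The secondary quality of life parameters will be the fourteen other scales of QLQ-C30 questionnaire and the eighteen scales" of the module. SAP 12.1.2 says: "Each parameter will be described at baseline. Changes of the scores from baseline of the parameters" will be provided, and puts the number at 15 for the QLQ-C30 and 13 for the module. Protocol 11.5.5.2 has the same phrase, "Changes of the scores from baseline of the parameters", with the same two numbers. The table list in SAP Appendix 1 (15.1) has one summary table for the module's single items, 14_5_2b: ("Single items) : Values and changes from baseline Over Time and at last cycle". Protocol 11.5.1 limits secondary work to description and names its scope: "secondary analyses on primary and secondary parameters, subgroup analyses, QoL".

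**The concern.** The divisor in such a score should equal the item's range, the highest code minus the lowest. The SAP follows this elsewhere: it divides by 3 for items coded 1 to 4 and by 6 for the two global health items coded 1 to 7. For items coded 1 to 2 the range is 1, yet the SAP divides by 3. The formula then contradicts the 0 to 100 range stated in the same section.

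At stake is the readability of descriptive tables. If the five items enter table 14_5_2b, they would stand beside six correctly scaled single items on the same nominal scale, with nothing in the table to reveal the difference. An arm difference in feeding-tube use, for instance, would appear at one third of its size.

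**Working it through.** **Inputs.** Formulas and stated range: SAP 6.2. Response codes: Protocol Appendix 7. Parameter counts: SAP 6.2, 6.2.2 and 12.1.2, and Protocol 11.5.5.2.

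**Stated range, checked by item type.** Score = (Q − 1)/divisor × 100 at the lowest and highest code:

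| Item type | Codes | SAP divisor | Lowest | Highest |
|---|---|---|---|---|
| Four-point | 1 to 4 | 3 | 0 | (4 − 1)/3 × 100 = 100 |
| Seven-point (global health) | 1 to 7 | 6 | 0 | (7 − 1)/6 × 100 = 100 |
| Yes/no (Q31 to Q35) | 1 to 2 | 3 | 0 | (2 − 1)/3 × 100 = 33.3 |
| Yes/no, divisor = range | 1 to 2 | 1 | 0 | (2 − 1)/1 × 100 = 100 |

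The 0 to 100 range is reproduced for the first two types and not for the five yes/no items. A divisor of 1 restores it.

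**Effect on summaries.** With a share p answering Yes, the mean is 33.3p under the SAP formula and 100p with the correct divisor. The shares below are assumptions, as the documents give none:

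| Assumed share Yes | Mean, SAP formula | Mean, divisor 1 |
|---|---|---|
| 20% | 6.7 | 20 |
| 50% | 16.7 | 50 |
| 80% | 26.7 | 80 |

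The SD of a two-valued score is largest at p = 0.5: about 33.3 × 0.5 = 16.7 under the SAP formula and 100 × 0.5 = 50 with divisor 1. A change from baseline, if summarised, can only be −33.3, 0 or +33.3 instead of −100, 0 or +100.

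**Counts.** The module has 7 multi-item scales + 6 four-point single items = 13; adding the 5 yes/no items gives 18. With the 15 QLQ-C30 scales the total is 33, so 5 of 33 scales are affected. The 13 change parameters would fit leaving out the five yes/no items, but neither document says that they are left out.

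**Separate check: module completeness.** SAP 7.5.2 requires at least two thirds of the questions and puts this at 23. Two thirds of 35 is 23.33, so 23 answers (23/35 = 65.7%) fall short. A form with exactly 23 answers is treated as follows:
- SAP 7.5.2: it counts towards evaluability.
- SAP 6.2 (more than two thirds must be answered): it is ignored.
- SAP 12.1.2 (more than one third missing): 12/35 = 34.3% missing, so it is non-evaluable.

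With 24 answers (24/35 = 68.6%) the three rules agree.

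**The case against.** The strongest reply is that the wrong scores may never be printed. Table 14_5_2b is the only listed summary table for the module's single items, and the listing of derived module scores is titled for multi-item scales only. The count of 13 suggests that the five items are left out of the change summaries. This is a fair limit on reach, and the effect on the change tables is therefore conditional. It does not remove the point. SAP 6.2.2 keeps all eighteen scales as parameters, SAP 12.1.2 describes each parameter at baseline, and the title of 14_5_2b makes no exception.

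A second reply is that dividing a yes/no item by 3 is a constant rescaling, equal in both arms. The share answering Yes can be recovered as the mean divided by 33.3, and the module answers are listed separately. This is correct and is why the point is minor. A reader must still know of the error to undo it.

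Third, Protocol 11.5.5.2 still announces a repeated measures analysis of all scales and single items, so quality of life might not be purely descriptive. Protocol 11.5.1 restricts it to description, and SAP 8.6 drops the model under amendment 11.

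Finally, the completeness slip is a different matter from the divisor, and changing 23 to 24 does not settle everything. A QLQ-C30 form with exactly 20 of 30 answers is accepted by SAP 7.5.1, ignored by SAP 6.2 (not more than two thirds) and not excluded by SAP 12.1.2 (10 of 30 missing is not more than one third). That objection stands. It concerns the wording of the threshold and is independent of the scoring error.

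**Conclusion.** The concern holds, as a minor error. As written, the formula for Q31 to Q35 gives 33.3 for Yes, one third of the score implied by the SAP's own range. It affects 5 of 18 module scales. The conclusion rests on the codes printed in Protocol Appendix 7 and on the absence of any recode in either document. It does not depend on the assumed shares, which only illustrate size.

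The baseline description is affected as the text stands. Whether change scores are affected depends on the unexplained difference between 13 and 18. Overall survival, safety, the multi-item scales and the primary quality of life parameter (global health status) are not touched by the scaling error, and the direction of any arm difference is preserved. The slip in SAP 7.5.2 is real but reaches only module forms with exactly 23 answers.

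**What to change.** - **SAP 6.2:** score Q31 to Q35 as (Q − 1) × 100. Reporting n (%) Yes at each visit instead of a score would serve equally well.
- **SAP 12.1.2:** state how the five items are shown, so that 13 and 18 agree. For example: changes are given for the 7 multi-item scales and the 6 four-point single items (13 in all), and Q31 to Q35 are shown as n (%) Yes per visit. If the sponsor intends something else by 13, the text should say so.
- **SAP 7.5.2:** replace 23 by 24. Using one form of the two-thirds rule in SAP 6.2, 7.5 and 12.1 would also settle the QLQ-C30 form with exactly 20 answers.

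The cost is a few lines of SAP text and five lines of scoring code, with no new data. If the quality of life tables already exist, those showing these items should be rerun.

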**Multi-item scales/Items:**

- Pain:  $((Q1+Q2+Q3+Q4)/4-1)/3 * 100$
- Swallowing:  $((Q5+Q6+Q7+Q8)/4-1)/3 * 100$
- Senses problems:  $((Q13+Q14)/2-1)/3 * 100$
- Speech problems:  $((Q16+Q23+Q24)/3-1)/3 * 100$

Trouble with social eating:  $((Q19+Q20+Q21+Q22)/4-1)/3 * 100$

Trouble with social contact:  $((Q18+Q25+Q26+Q27+Q28)/5-1)/3 * 100$

Less sexuality:  $((Q29+Q30)/2-1)/3 * 100$

### **Single items:**

Teeth:	$(Q9-1)/3 * 100$
Opening mouth:	$(Q10-1)/3 * 100$
Dry mouth:	$(Q11-1)/3 * 100$
Sticky saliva:	$(Q12-1)/3 * 100$
Coughing:	$(Q15-1)/3 * 100$
Felt ill:	$(Q17-1)/3 * 100$
Pain killers :	$(Q31-1)/3 * 100$
Nutritional supplements:	$(Q32-1)/3 * 100$
Feeding tube:	$(Q33-1)/3 * 100$
Weight loss:	$(Q34-1)/3 * 100$
Weight gain:	$(Q35-1)/3 * 100$

If a question was filled in by circling more than one answer, the internal convention at Pierre Fabre is to consider the answer as missing.

A questionnaire is considered to be completed if more than two thirds of the questions are answered. Otherwise the questionnaire is ignored for the analysis.

#### **6.2.1. Primary parameter**

The primary quality of life parameter will be the global health status.

#### **6.2.2. Secondary parameter**

The secondary quality of life parameters will be the fourteen other scales of QLQ-C30 questionnaire and the eighteen scales of the QLQ-H&N 35 EORTC. Each analysis will be presented by functional and/or "symptoms" scales for QLQ-C30 questionnaire and by multi-items scales and/or single items for the QLQ-H&N 35 EORTC.

#### **6.2.3. Windows**

The Quality of life of a patient at the time of an administration will be based on the answers provided by the patient in the last questionnaire completed and evaluable.

At baseline, only questionnaires which were completed within the window of seven days prior to the randomisation (and including any questionnaire filled that day) will be considered. If more than one questionnaire is available within this window the last non-missing questionnaire will be analysed.

Any questionnaire that would be completed after the date of last administration plus 30 days therefore out of study treatment (not as per protocol) would not be analysed.

### **6.3. FURTHER ANTI-CANCER THERAPY**

Further anti-cancer therapies include any anti-tumour treatment given to the patient after withdrawal from study drug treatment.

## **7. DEFINITION OF POPULATIONS**

### **7.1. INTENT-TO-TREAT POPULATION (ITT)**

All randomised patients will be included in the Intent-To-Treat (ITT) population. They will be analysed in the arm they were assigned by randomisation.

### **7.2. ELIGIBLE POPULATION**

Following the protocol amendment 11, the eligible population will not be defined and used.

### **7.3. EVALUABLE POPULATION FOR RESPONSE**

Following the protocol amendment 11, the evaluable population for response will not be defined and used.

### **7.4. EVALUABLE POPULATION FOR SAFETY**

All randomised and treated patients will be included in the safety analysis. They will be analysed in the treatment arm they actually received.

### **7.5. EVALUABLE POPULATION FOR HEALTH-RELATED QUALITY OF LIFE ASSESSMENT**

#### **7.5.1. Evaluable population for QLQ-C30**

To be evaluable for the QLQ-C30 questionnaire, randomised patients should have completed at least two thirds (i.e. at least 20 questions) of the questions of the baseline QLQ-C30 questionnaire within 7 days prior to randomisation, and at least two thirds of the questions of a QLQ-C30 questionnaire during the study period or at the end of study (during last cycle).

#### **7.5.2. Evaluable population for QLQ-H&N 35 EORTC module**

To be evaluable for the QLQ-H&N 35 EORTC module, randomised patients should have completed at least two thirds of the questions (i.e. at least 23 questions) of the baseline the QLQ-H&N 35 EORTC

module within 7 days prior to randomisation, and at least two thirds of the questions of a QLQ-H&N 35 EORTC module during the study period or at the end of study (during last cycle).

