8.4. QUALITY OF LIFE

- During the course of the study, the patients will be asked to complete the QLQ-C30 questionnaire and the QLQ-H & N 35 module to measure the health-related quality of life.

Support for the reliability and validity of the QLQ-C30 questionnaire and the QLQ H & N 35 module has been reported in the published literature.

- The QLQ-C30 questionnaire and the QLQ-H & N 35 module will be completed prior to randomisation (within 24 hours), every 6 weeks and at the end of treatment evaluation.
- Patients will be considered evaluable for health-related quality of life analysis if they have completed at least 2 questionnaires (including the questionnaire completed within 24 hours prior to randomisation). Of note, if local language is not available the patient will not be evaluable.

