11.3.5. Evaluable population for health-related quality of life assessment

To be evaluable for health-related quality of life assessment, patients should have completed one questionnaire (at least two third of the questions) within seven days prior to randomisation, and at least one questionnaire (at least two third of the questions) during the study period. To be considered evaluable, the questionnaires should be available in the native language of the patient, otherwise, the patient will not be evaluable for quality of life.

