### 6.2. QUALITY OF LIFE PARAMETERS

The European Organisation for Research and Treatment of Cancer (EORTC) score questionnaire (QLQ-C30) will be analysed as well as the QLQ-Head and Neck 35 EORTC module, to measure the health-related quality of life.

The QLQ-C30 and the QLQ-Head and Neck 35 EORTC module will be completed prior to randomization, every 6 weeks and at the end of treatment evaluation.

Health-related quality of life parameters will be the fifteen scales that can be derived from the 30 questions of the EORTC QLQ-C30 questionnaire:

- A global health-related quality of life scale,
- Five functional scales: physical, role, cognitive, emotional, social,
- Nine symptom scales: nausea and vomiting, pain, fatigue, dyspnoea, insomnia, appetite loss, constipation, diarrhoea, financial difficulties.

Of note, a higher value in functional scales will reflect a better level of function, but for "symptoms" scales a higher value will reveal a deterioration of the condition.

Each scale in the EORTC QLQ-C30 questionnaire will be scored (0 to 100) according to the EORTC recommendations in the EORTC QLQ-C30 Scoring Manual. The scoring method is summarized below. In this summary Qi refers to the  $i^{\text{th}}$  question on the EORTC QLQ-C30.

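### SAP 7.5.2 sets the QLQ-H&N35 threshold at 23 of 35 answers, which is below its own two-thirds rule, and SAP 6.2 discards a QLQ-C30 form with exactly 20 of 30 answers that SAP 7.5.1 accepts

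*SAP*

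**What the plan says.** The SAP and protocol set a minimum number of answered items for a quality-of-life form in several places.

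- SAP 7.5.2 (QLQ-H&N35 population): the baseline form must have "at least two thirds of the questions (i.e. at least 23 questions" answered. An on-study form must also reach two thirds, with no count given.
- SAP 7.5.1 (QLQ-C30 population): the baseline form must have "at least two thirds (i.e. at least 20 questions) of the questions" answered.
- SAP 6.2, at the end of the scoring rules: "A questionnaire is considered to be completed if more than two thirds of the questions are answered". A form that fails this is left out of the analysis.
- SAP 12.1.2: "if more than one third of the items is missing then the questionnaire is non-evaluable".
- SAP 12.1.1 and protocol 11.3.5: two thirds or more, with no count.

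On timing, the third bullet of protocol 8.4 calls a patient evaluable after having "completed at least 2 questionnaires (including the questionnaire completed within 24 hours prior to randomisation". Protocol 11.3.5 defines the same evaluability with a baseline form completed "within seven days prior to randomisation". SAP 6.2.3, 7.5.1, 7.5.2 and 12.1.1 all use seven days.

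**The concern.** These rules decide who is in each quality-of-life population and which forms are scored. The only threshold for the QLQ-H&N35 that is stated as a count does not satisfy the fraction that it is meant to express. For the QLQ-C30, the count named as sufficient is exactly the one at which another section throws the form away. A programmer cannot obey both rules for such a form, and two programmers could reach different numbers.

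Change in disease-related symptoms on the EORTC questionnaires is a stated secondary objective. The number evaluable for quality of life is reported in table 10_1a (SAP Appendix 1), and tables 14_5_1a to 14_5_2b are labelled by the two evaluable populations. If the population is built from section 7.5 and the scores from section 6.2, the reported N and the patients who contribute a change from baseline can differ.

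**Working it through.** **Inputs.** The QLQ-C30 has 30 questions: SAP 6.2 refers to "the fifteen scales that can be derived from the 30 questions of the EORTC QLQ-C30 questionnaire". The head and neck module has 35: "Eighteen scales are derived from the 35 questions of the QLQ-H&N 35 EORTC module". The rules are those listed above.

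**Formulas.** For n items, the smallest count that is at least two thirds is 2n/3 rounded up. The smallest count that is strictly more than two thirds is 2n/3 rounded down, plus 1. The missing-item rule in SAP 12.1.2 (a form fails if more than one third is missing) is the same as requiring at least two thirds answered.

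**Reproducing the plan's counts.**

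- QLQ-C30: 2 × 30 / 3 = 20.00. Rounded up this is 20, so the stated 20 reproduces.
- QLQ-H&N35: 2 × 35 / 3 = 23.33. Rounded up this is 24, so the stated 23 does not reproduce. Rounding down or to the nearest integer gives 23, which is the likely origin of the figure.

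**Applying each rule at the boundary.**

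| Form | Answered | Missing | SAP 7.5 stated count | At least two thirds (7.5, 12.1.1, protocol 11.3.5) | 12.1.2 | 6.2 (strict) |
|---|---|---|---|---|---|---|
| QLQ-H&N35, 23 of 35 | 65.71% | 12/35 = 34.29% | passes | fails | fails | fails |
| QLQ-H&N35, 24 of 35 | 68.57% | 11/35 = 31.43% | passes | passes | passes | passes |
| QLQ-C30, 20 of 30 | 66.67% | 10/30 = 33.33% | passes | passes | passes | fails |
| QLQ-C30, 21 of 30 | 70.00% | 9/30 = 30.00% | passes | passes | passes | passes |

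Two things follow. For the QLQ-H&N35 the strict and non-strict rules both give 24, because two thirds of 35 is not a whole number; the only fault there is the 23. For the QLQ-C30 the stated count is right, and the fault is the strict wording of SAP 6.2, which would need 21.

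**Baseline window, side by side.** The 24-hour window stands in the protocol flow chart (Table 1), in Table 18, and in the second and third bullets of section 8.4. The first three of these say when to collect the form. Only the third bullet of 8.4 is a rule on who is evaluable, and it conflicts with the seven days in protocol 11.3.5. A form completed more than 24 hours but no more than 7 days before randomisation meets 11.3.5 and every SAP rule on timing, but not 8.4.

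**The case against.** Four arguments can be made for leaving the text alone.

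*The words of 7.5.2 already exclude a 23-answer form, and only the parenthesis admits it.* This is true, and a careful programmer might use 24. But the parenthesis is the part that gets coded, and the section contradicts itself, so it still needs correcting.

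*The effect is tiny.* This stands. Each conflict touches one exact number of answers. Protocol 11.5.1 makes the quality-of-life analysis descriptive, and SAP 8.6 drops the repeated-measures analysis, so no test depends on it.

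*A 24-hour collection window with a wider analysis window is not a contradiction.* This holds for the flow chart, Table 18 and the second bullet of 8.4. It does not hold for the third bullet of 8.4, which defines evaluability.

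*Editing protocol 8.4 needs a formal amendment after recruitment has closed.* Protocol 15.1 does require one, so the window is better settled in the SAP.

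A reader might also infer more than the documents support. One such inference is that the window conflict moves a material number of patients in or out of the quality-of-life tables. It does not: the SAP applies seven days in every section that mentions a baseline window, and tables 10_1a and 14_5_1a to 14_5_2b come from the SAP's list. The documents also give no distribution of form completion dates from which to count patients. Another is that a patient could enter the QLQ-H&N35 population with no usable form at all. The 23 is attached only to the baseline form; the on-study form must reach two thirds on its own, so what is lost is the baseline.

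**Conclusion.** The threshold of 23 in SAP 7.5.2 is wrong as written; the count that satisfies the rule is 24. A patient whose only baseline QLQ-H&N35 form has exactly 23 answers is admitted by that count but has no usable baseline under SAP 12.1.2 or 6.2, and so no change from baseline. SAP 6.2 also conflicts with SAP 7.5.1, 12.1.1, 12.1.2 and protocol 11.3.5 for a QLQ-C30 form with exactly 20 answers.

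The size is small. Only forms with exactly 23 of 35 or exactly 20 of 30 answers are affected. That these are probably few is a judgement, since the documents do not report item completion. The primary analysis of overall survival is not touched.

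The difference between protocol 8.4 and protocol 11.3.5 on the baseline window is real but secondary. It is a conflict within the protocol, and between one bullet of it and the SAP. It changes no SAP table as long as the seven-day rule is applied.

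**What to change.** 1. In SAP 7.5.2, change 23 to 24.
2. In SAP 6.2, change *more than* two thirds to *at least* two thirds. This matches SAP 7.5.1, 7.5.2, 12.1.1, 12.1.2 and protocol 11.3.5, and keeps 20 of 30 as the QLQ-C30 minimum.
3. Add one sentence to the SAP stating that the seven-day window before randomisation governs the quality-of-life analysis, and that the 24 hours in the protocol is the collection window.

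The cost is two wording edits, one programming constant and one added sentence. No new data are needed, and no protocol amendment is needed if the window is settled in the SAP. At most the evaluable count shifts very slightly. The third change moves no patient in the SAP tables.
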